**Table 10-1 Protocol-Required Laboratory Assessments**

Test Category	Notes
All Subjects - Local Laboratory	
Hematology	Hemoglobin, hematocrit, CBC including WBC differential (neutrophils, basophils, eosinophils, lymphocytes, monocytes [absolute values for differential are preferred]) reticulocytes and platelets
Biochemistry	Albumin, alkaline phosphatase, ALT, AST, bicarbonate, LDH, calcium, chloride, magnesium, inorganic phosphorus (phosphate), sodium, potassium, creatinine, total and direct bilirubin, BUN or urea, uric acid, glucose (non-fasting), total protein
Coagulation	INR, aPTT, PT, fibrinogen
Urinalysis	
 
pH, glucose, protein, blood, ketones, bilirubin, urobilinogen, nitrite, leukocyte esterase, specific gravity.
 

β2-microglobulin	At Screening only.
Pregnancy test (serum or urine)	For female subjects with reproductive potential, a serum pregnancy test (β-hCG) should be performed at Screening, and a urine or serum test at the start of each cycle and at the end of treatment visit.
Serology	
 
At Screening only.
 
HBV: HbsAg, anti-HBs, and anti-HBc.
 
HCV: HCV antibody. If positive serology PCR for HCV-RNA to be performed.
 
CMV serology (IgG and IgM) at Screening. If positive, further surveillance, ie, PCR for CMV-DNA to be performed at the investigator's discretion.
 
HIV: Performed at Screening only if required per local health authorities or institutional standards (see Section 10.15.1).
 

Tumor lysis (TLS) sample	Uric acid, potassium, inorganic phosphorus (phosphate), calcium, and serum creatinine.
Bone marrow biopsy and/or aspirate	For subject response assessments, perform locally, a portion will be sent to central laboratory (see below).
Blood type assessment	At Screening only. See Section 8.3.6.3.
Cytogenetics	At Screening only. For subjects with RRMM see Section 8.1.2.1, R/R AML see Section 8.1.2.2, and R/R DLBCL see Section 8.1.2.3.
Molecular mutational status	At Screening only. For subjects with RRMM see Section 8.1.2.1, R/R AML see Section 8.1.2.2, and R/R DLBCL see Section 8.1.2.3.
All Subjects - Central Laboratories	
PK	
ADA	
Biomarkers	
MRD 	
 
- For subjects with RRMM, collect in Dose Escalation and Expansion.
 
- For subjects with R/R AML or R/R DLBCL, only collect in Expansion.
 

Genomic DNA-seq control sample (saliva)	At Screening only. See Section 8.8.2.6.

(continued on next page)

Subjects with RRMM	
Local Laboratory	
Serum calcium corrected for albumin	From biochemistry panel. See Section 10.7 for formula to perform calculation.
Quantitative serum Ig panel (IgA, IgG, IgM, IgE, and IgD)	At Screening and time points listed on Table 1-1, Table 1-5, and Table 1-12
SPEP and UPEP (24-h urine sample) and interference assay sample, serum FLC, and serum/urine IFE	At Screening only.
Bone marrow aspirate and/or bone marrow biopsy	At Screening for disease assessment and to confirm CR/sCR
Central Laboratories	
SPEP and UPEP (24-h urine sample) and interference assay sample	At Screening and time points listed on Table 1-1, Table 1-5, and Table 1-12.
Serum FLC and serum/urine IFE	At Screening and at the time when CR/sCR is suspected or maintained. Perform serum FLC on Day 1 of every cycle for all subjects.
Bone marrow aspirate	To assess MRD, and for biomarker evaluations
Subjects with R/R AML	
Local Laboratory	
Peripheral blood assessment	AML blast cell count and CBC with differential including promyelocytes, myelocytes, and metamyelocytes.
Immunoglobulins (IgA, IgG, IgM)	At Screening only.
Bone marrow assessment	Bone marrow assessment for diagnosis and response.
Central Laboratories	
Bone marrow aspirate	
Subjects with R/R DLBCL	
Local Laboratory	
Immunoglobulins (IgA, IgG, IgM)	At Screening only.
Central Laboratories	
-	

ADA=anti-drug antibody; ALT=alanine aminotransferase; AML=acute myeloid leukemia; anti-HBc=antibodies to the hepatitis B core antigen; anti-HBs=antibodies to the hepatitis B surface antigen; aPTT=activated partial thromboplastin time; AST=aspartate aminotransferase;  $\beta$ -hCG=beta-human chorionic gonadotropin; BUN=blood urea nitrogen; CBC=complete blood count; CMV=cytomegalovirus; CR=complete remission; CCI; DNA=deoxyribonucleic acid; FLC=free light chain; h=hour(s); HBsAg=hepatitis B surface antigen; HBcAb=hepatitis B core antibody; HBV=hepatitis B virus; HCV=hepatitis C virus; HIV=human immunodeficiency virus; IFE=immunofixation; Ig=immunoglobulin; INR=international normalized ratio; LDH=lactate dehydrogenase; MRD=minimal residual disease; PCR=polymerase chain reaction; PK=pharmacokinetic(s); PT=prothrombin time; RNA=ribonucleic acid; R/R AML=relapsed or refractory acute myeloid leukemia; R/R DLBCL=relapsed or refractory diffuse large B-cell lymphoma; RRMM=relapsed or refractory multiple myeloma; sCR=stringent complete response; seq=sequencing; SPEP=serum protein electrophoresis; TLS=tumor lysis syndrome; UPEP=urine protein electrophoresis; WBC=white blood cell.

## **10.3 Appendix 3: Adverse Events: Definitions and Procedures for Recording, Evaluating, Follow-up, and Reporting**

### **10.3.1 Definitions**

#### **Definition of Adverse Events**

An AE is any untoward medical occurrence in a patient or clinical trial subject, temporally associated with the use of a medicinal product, whether or not considered related to the medicinal product. An AE can therefore be any unfavorable and unintended sign (including an abnormal laboratory finding), symptom, or disease (new or exacerbated) temporally associated with the use of a medicinal product.

AEs (including laboratory abnormalities that constitute AEs) should be described using a diagnosis whenever possible, rather than individual underlying signs and symptoms. When a clear diagnosis cannot be identified, each sign or symptom should be reported as a separate AE.

#### **Definition of Serious Adverse Events**

An SAE is defined as an AE that meets 1 of the following criteria:

- Is fatal or life-threatening
- Results in persistent or significant disability/incapacity
- Constitutes a congenital anomaly/birth defect
- Is medically significant, ie, defined as an event that jeopardizes the subject or may require medical or surgical intervention to prevent one of the outcomes listed above
- Requires inpatient hospitalization or prolongation of existing hospitalization

 The term "life-threatening" in the definition of "serious" refers to an event in which the subject was at risk of death at the time of the event; it does not refer to an event which hypothetically might have caused death if it were more severe.

 Hospitalizations for the following reasons should not be reported as SAEs:

- Routine treatment or monitoring of the underlying disease
- Solely due to progression of the underlying cancer
- Elective or pre-planned treatment for a pre-existing condition that is unrelated to the underlying disease and has not worsened since signing the informed consent
- Social reasons and respite care in the absence of any deterioration in the subject's general condition
- Treatment on an emergency outpatient basis that does not result in hospital admission and involves an event not fulfilling any of the definitions of a SAE given above is not an SAE.

#### **Definition of Adverse Events of Special Interest**

AESIs are defined as events (serious or non-serious) which are of scientific and medical concern specific to the sponsor's product or program, for which ongoing monitoring and rapid communication by the investigator to the sponsor may be appropriate. Such events may require further investigation in order to characterize and understand them. IRRs will be considered

AESIs for GEN3014. Other AESIs are defined on the basis of an ongoing review of the safety data.

### **Definition of Infusion-Related Reactions**

IRRs are defined as any AEs occurring during infusion or where the onset of the event occurs within 24 hours after the end of the GEN3014 infusion. For IRRs, the causality of the event should be judged as “related” by the investigator.

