**Table 1-12 Schedule of Activities – Subjects with RRMM – Expansion Part B (Randomized H2H)**

Cycle(s)	Pro- tocol Section	Notes	Screen- ing	Q1W (Weekly)					Q2W		Q4W	UNS	End of Treat- ment	Safety Follow- up 	Survival Status/ contact 
				Cycles 1-2					Cycles 3-6		Cycle 7 onward				
Cycle Day			D -21 to D -1	D1 	D2 (C1 only, GEN- 3014)	D8	D15	D22	D1	D15	D1		ASAP after last dose	30d after last dose	Q3M
Visit Window							±3d		±3d		±3d		+7d	+7d	±7d
Informed consent	10.1.5	Obtain prior to any trial-related activity	X												
Eligibility criteria	5.1, 5.2		X												
Demographics	8.1.1		X												
Medical history 	8.1.3		X 	X											
Disease status	8.1.2	Includes diagnosis and staging criteria	X												
Constitutional symptoms	8.3.7	At Screening and before trial drug dosing	X	X		X	X	X	X	X	X				
ECOG PS	8.3.5		X	X					X		X	X	X		
Prior anti-cancer therapy	6.7.1		X												
Prior/concomitant medications and therapies	6.7		X	X	X	X	X	X	X	X	X	X	X		
Height	8.3.2		X												
Body weight	8.3.2	Measure weight within 72 h before GEN3014 infusion	X	X		X	X	X	X	X	X	X			

Cycle(s)	Pro- tocol Section	Notes	Screen- ing	Q1W (Weekly)					Q2W		Q4W	UNS	End of Treat- ment	Safety Follow- up 	Survival Status/ contact 
				Cycles 1-2					Cycles 3-6		Cycle 7 onward				
Cycle Day			D -21 to D -1	D1 	D2 (C1 only, GEN- 3014)	D8	D15	D22	D1	D15	D1		ASAP after last dose	30d after last dose	Q3M
Visit Window							±3d		±3d		±3d		+7d	+7d	±7d
Vital signs	8.3.3	On trial drug dosing days, as per Section 8.3.3. At Safety Follow-up visit as required per local health authorities (see Section 10.15).	X	X	X	X	X	X	X	X	X	X	X	X	
Physical examination	8.3.1	At Screening, perform complete physical exam. At subsequent visits, a symptom-directed/ clinically indicated (brief) physical examination may be performed. At Safety Follow-up visit as required per local health authorities (see Section 10.15).	X	X					X		X		X	X	
12-Lead ECG	8.3.4	Perform in triplicate	X	X		X	X	X	X		X	X	X		
Adverse Events 	8.4		X 	X	X	X	X	X	X	X	X	X	X	X 	
TRIAL DRUG ADMINISTRATION															
Post-administration Monitoring 	6.2.5			X  (C1)	X  (C1)	X  (C1)	X  (C1)	X  (C1)							

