UNS			X	X	X	X	X		X		

ADA=anti-drug antibody; C=cycle; D/d=day; DNA=deoxyribonucleic acid; h=hour(s); H2H=head-to-head; min=minutes; PBMCs=peripheral blood mononuclear cells; PK=pharmacokinetic(s); RNA=ribonucleic acid; seq=sequencing; UNS=unscheduled.

1. After flush.
2. ADA and biomarker samples in even cycles only.
3. Cycle 2 only.
4. For RRMM: collect sample at C4D1 only. Testing at these time points is for immunophenotyping only.
5. Collect if clinically feasible.

**Table 1-14 Schedule for PK, Biomarker/Pharmacodynamic, and Immunogenicity Sampling – Daratumumab SC-Treated Subjects – Expansion Part B (Randomized H2H)**

Cycle (28-day cycles)	Day (Window)	Time Point (Window)	PK	ADA	Cyto- kines	Comple- ment	Immuno- pheno- typing	Pro- teomics	Explora- tory PBMCs	DNA- seq control sample (saliva)	Bone Marrow for Immuno- phenotyping and DNA/ RNA seq
Screening	Day -21 to Day -1			X						X	X
Cycle 1	Day 1	Predose (-30 min)	X	X	X	X	X	X	X		
		End of injection +4 h (±30 min)			X	X					
	Day 2	End of injection +24 h (±2 h)	X		X	X	X				
	Day 4	End of injection +72 h (±24 h)	X				X				
	Day 8	Predose (-30 min)	X		X	X	X	X			
	Day 15	Predose (-30 min)	X			X	X	X			
Cycle 2 to Cycle 6	Day 22	Predose (-30 min)	X	X		X	X	X			
	Day 1	Predose (-30 min)	X	X 			X	X	X		X 
	Day 8 (+2d)	Predose (-30 min)	X 								
	Day 15 (+2d)	Predose (-30 min)	X				X				
	Day 22 (+2d)	Predose (-30 min)	X 								
	Day 23	End of injection +24 h (±2 h)	X 								
Cycle 7 and Beyond	Day 25	End of injection +72 h (±24 h)	X 								
	Day 1 (+3d)	Predose (-30 min)	X	X 			X 		X 		
End of Treatment			X	X				X			X 
UNS			X	X	X	X	X		X		

ADA=anti-drug antibody; C=cycle; D/d=day; DNA=deoxyribonucleic acid; h=hour(s); H2H=head-to-head; min=minutes; PBMCs=peripheral blood mononuclear cells; PK=pharmacokinetic(s); RNA=ribonucleic acid; SC=subcutaneous; seq=sequencing; UNS=unscheduled.

1. ADA and biomarker samples in even cycles only.
2. Cycle 2 only.
3. Collect sample at C4D1 only. Testing at this time point is for immunophenotyping only.
4. Collect if clinically feasible.

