**Table 3-3 Objectives and Endpoints – Expansion Part B (Randomized H2H)**

Objectives	Endpoints
Primary	

 
Compare overall response of GEN3014 IV vs daratumumab SC in anti-CD38 mAb-naïve RRMM subjects
 
	
 
ORR
 

Secondary	

 
Compare PK between GEN3014 IV vs daratumumab SC
 
	
 
Ctrough levels of GEN3014 IV, or daratumumab SC, on Cycle 3 Day 1
 

 
Assess the anti-tumor activity of GEN3014 IV vs daratumumab SC
 
	
 
VGPR or better
 
CR or better
 
DOR
 
TTR
 
PFS
 
OS
 
Time to next therapy (TTNT)
 

 
Assess safety of GEN3014 IV vs daratumumab SC
 
	
 
Safety: Incidence and severity of AEs and SAEs, including changes in laboratory values, vital signs, ECGs
 
Immunogenicity: Anti-GEN3014 antibodies, anti-daratumumab antibodies
 

Exploratory	

 
Evaluate the pharmacodynamic profiles of GEN3014 and compare with those of daratumumab
 
	
 
Pharmacodynamic markers in blood and tumor samples, including frequencies of NK cells and other leukocyte subsets, and complement analyses
 

 
Assess potential biomarkers predictive of clinical response to GEN3014 and evaluate potential surrogacy with PFS and OS
 
	
 
CCI [REDACTED]
 
CCI [REDACTED]
 
CCI [REDACTED]
 

 
Assess MRD status
 
	
 
Rate and duration of MRD-negative remission
 

 
Explore PK/pharmacodynamic relationship (PK/anti-tumor activity) and PK/safety
 
	
 
Dose concentration response (biomarkers and/or efficacy, safety) relationship
 

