#### **6.2.4 Management of sARRs and Local Injection Site Reactions of Daratumumab SC**

##### **6.2.4.1 Systemic Administration-Related Reactions**

Systemic administration-related reactions are systemic reactions related to daratumumab administration. Subjects should be observed carefully during daratumumab administrations. Trained study staff at the clinic should be prepared to intervene in case of any sARRs, and resources necessary for resuscitation (eg, agents such as epinephrine and aerosolized bronchodilator, medical equipment such as oxygen tanks, tracheostomy equipment, and a defibrillator) must be available at the bedside. Attention to staffing should be considered when multiple subjects will be dosed at the same time.

If an sARR develops during daratumumab SC administration, then the administration should be temporarily interrupted. Subjects who experience AEs during daratumumab administration must be treated for their symptoms. Subjects should be treated with paracetamol (acetaminophen), antihistamine, or corticosteroids, as needed. IV saline may be indicated. For bronchospasm, urticaria, or dyspnea, subjects may require antihistamines, oxygen, corticosteroids, or bronchodilators. For hypotension, subjects may require vasopressors. In the event of a life-threatening sARR (which may include pulmonary or cardiac events) or an anaphylactic reaction, daratumumab should be permanently discontinued.

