#### 5.5.2.3 *Adverse Events of Special Interest*

IRRs will be considered as AESIs for GEN3014. The corresponding AESI for subcutaneous daratumumab SC are systemic administration-related reactions (sARR).

The number and percentage of subjects with treatment emergent adverse event of special interest will be presented by SOC, PT and worst toxicity grade. Additionally, the number and percentage of subjects with treatment emergent adverse event of special interest leading to treatment discontinuation and dose interruption will be summarized. Time to onset of first IRR, and time to resolution (for resolved cases) will be presented.

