### **5.5.3      *Treatment Emergent Fatal AEs and Deaths***

The number and percentage of subjects who died due to related TEAE will be summarized by PT. All fatal adverse events will be presented in a separate listing, indicating relationship to treatment.

All deaths as reported on the eCRF death form will be summarized by primary cause of death. In addition, deaths occurring within 30 or 60 days of first GEN3014 dose, or within 30 or 60 days of last GEN3014 dose will be summarized by primary cause of death.

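### Three Part B safety summaries (administration reactions, Cycle 1 Day 2 labs and vital signs, 30/60-day deaths) are not like for like between GEN3014 and daratumumab

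*Protocol*

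**What the plan says.** Protocol Table 3-3 lists as a Part B secondary objective "Assess safety of GEN3014 IV vs daratumumab SC". No test is planned, so the per-arm summaries are the answer.

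**Reactions.** Protocol Section 10.3.1, on GEN3014 infusions: "IRRs are defined as any AEs occurring during infusion or where the onset of the event occurs within 24 hours after the end". It adds that for IRRs "the causality of the event should be judged as" related by the investigator. Section 6.2.4.1, for the other arm: "Systemic administration-related reactions are systemic reactions related to daratumumab administration". No time window is given there, and local injection-site reactions are a separate category (Section 6.2.4.5). SAP 5.5.2.3, having named IRRs as the AESI for GEN3014, continues: "The corresponding AESI for subcutaneous daratumumab SC are systemic administration-related reactions (sARR"). It specifies time to onset and time to resolution for IRRs only.

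**Day 2.** The Part B schedule (protocol Table 1-12) has a column headed "D2 (C1 only, GEN- 3014"). Vital signs, AE review, hematology, biochemistry, coagulation and TLS labs are marked in it. Daratumumab subjects are sampled on Day 2 at "End of injection +24 h (±2 h") under Table 1-14, but only for PK, cytokines, complement and immunophenotyping. SAP 5.5.4.1 summarises the worst post-baseline on-treatment lab grade. SAP 5.5.4.2 counts subjects who meet a vital-sign criterion at any post-baseline assessment.

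**Deaths.** SAP 5.5.3 summarises all deaths by primary cause, and in addition "deaths occurring within 30 or 60 days of first GEN3014 dose, or within 30 or 60 days of last GEN3014 dose". Daratumumab dosing is not mentioned.

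**The concern.** Part B is open-label and descriptive. A reader of the report will set the GEN3014 and daratumumab columns side by side and attribute the difference to the drugs. In these three places, part of the difference can come from the definition or the schedule.

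For reactions, one arm is counted by timing and the other by the nature of the event and its attribution. For labs and vital signs, a worst-value or ever-met summary rises with the number of looks, and only one arm has a scheduled look on the day after first dose. For early deaths, the comparator has no row, so the table cannot be read as a comparison at all.

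**Working it through.** **1. Reaction definitions side by side**

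| | IRR (GEN3014) | sARR (daratumumab) |
|---|---|---|
| Window | infusion plus 24 h | none |
| Event type | any AE | systemic only |
| Causality | to be judged related (ambiguous) | related |
| Onset and resolution times in SAP | yes | not specified |

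The causality sentence has two readings. Under reading A, every AE in the window is called related and becomes an IRR. Under reading B, an AE in the window is an IRR only if the investigator judges it related.

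Window time in Cycles 1–2 (56 days = 1344 h), with infusion length L = 1 to 8 h (Section 6.1.1) and Day 2 assumed to start 24 h after Day 1:
- GEN3014, Days 1 and 2 merged: 48 + L = 49 to 56 h.
- GEN3014, seven other infusions: 7 × (24 + L) = 175 to 224 h.
- GEN3014 total: 224 to 280 h, which is 16.7% to 20.8% of 1344 h.
- The same window applied to daratumumab, eight injections of 3–5 min (Section 6.1.2): 8 × 24 h plus under 1 h ≈ 193 h, or 14.4%.
- Ratio: 224/193 = 1.16 to 280/193 = 1.45.

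Under reading A, assume 0.5 to 2 background AEs per subject over 56 days, spread evenly (an assumption; the documents give no rate). The share of GEN3014 subjects with at least one AE labelled an IRR by timing alone is 1 − exp(−rate × fraction):
- 1 − exp(−0.5 × 0.167) = 8%
- 1 − exp(−2 × 0.208) = 34%

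Under reading B this timing-only mechanism does not operate. The difference in window and in event type remains, and because the sARR has no window it could favour either arm.

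**2. Scheduled looks (Table 1-12; Section 8.3.3 for vital-sign time points)**

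| | GEN3014 | Daratumumab |
|---|---|---|
| Lab sets after first dose, Cycle 1 | 4 (D2, D8, D15, D22) | 3 (D8, D15, D22) |
| Lab sets, Cycles 1–6, including C1D1 | 5 + 4 + 8 = 17 | 4 + 4 + 8 = 16 |
| Vital-sign readings, Cycle 1 | 5 × 5 = 25 | 5 × 4 = 20 |
| Vital-sign readings, Cycles 1–6 | 25 + 24 = 49 | 20 + 24 = 44 |

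Suppose toxicity is equal and each lab set independently shows a given abnormality with probability q (assumed). One extra set on top of k then raises the ever-abnormal proportion by q(1 − q)^k. For q = 0.02, 0.05, 0.10 and 0.20:
- Cycle 1 (k = 3): 1.9, 4.3, 7.3 and 10.2 percentage points.
- All six cycles completed (k = 16 − 1 = 15, leaving out C1D1): 1.5, 2.3, 2.1 and 0.7 points.

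The effect is therefore modest over a full course. It is largest for early, transient changes and for subjects who stop early.

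**3. Deaths.** The all-deaths summary (SAP 5.5.3) and OS from randomization (SAP 5.4.6) include daratumumab subjects. Only the 30/60-day breakdown has no anchor for them.

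**The case against.** Much is common to both arms: the AE reporting window (protocol Section 8.4.2), CTCAE grading and the SOC/PT summaries of TEAEs and SAEs, 4 h of Cycle 1 observation (Section 6.2.5), the ECG schedule, the safety follow-up visit and the all-deaths summary. A reader might infer that the whole Part B safety comparison is invalid. The documents do not support that.

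A reader might also infer that GEN3014 is bound to look worse on reactions. That needs reading A. Section 10.3.4 has the investigator judge every event related or not related, which fits reading B. Separate reaction terms for an IV and an SC product are also an ordinary convention, and the SAP plans no IRR-to-sARR ratio. This removes any claim about direction. It does not make the two definitions comparable.

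The Day 2 difference follows from the split first dose. Appendix 2 (Section 10.2) requires labs on the day before or the day of each administration, and vital signs are taken around each one. That explains the extra look without removing its effect on a worst-value summary. AE review is a weaker example, because AEs are collected continuously and Section 10.3.3.1 asks for re-assessment at each visit.

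The early-death wording looks like a drafting gap. The SAP is based on Amendment 3, and Amendment 5 later added daratumumab to parallel protocol text. It would still be programmed as written.

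Finally, the IRR rule might seem to distort the stopping guidance between arms. Section 9.6 excludes daratumumab subjects from that guidance, so it is not a between-arm matter.

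**Conclusion.** The point holds for three named summaries and no further.

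- **Reactions:** the IRR and sARR tables cannot be compared as they stand. Direction and size are uncertain until the causality sentence is clarified. The 8–34% applies only under reading A with the assumed background AE rate.
- **Labs and vital signs:** GEN3014 has one extra lab set and five extra vital-sign readings, all on Cycle 1 Day 2. The resulting artefact depends on an assumed detection probability and shrinks as later visits accumulate.
- **Early deaths:** the comparator has no 30/60-day row. To say that its early deaths go unreported would be too strong, since they are in the all-deaths summary and in OS.

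No alpha, power or sample-size figure is affected. The changes are worth making because they are cheap and alter what the comparison shows.

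**What to change.** **(a) SAP 5.5.2.3.** For Part B, add one drug-neutral table of TEAEs with onset from the start of administration to 24 h after its end, regardless of label or causality, with a prespecified term list defining which events count as systemic. A common window alone does not equalise time at risk, so show results per subject, per administration and for the first dose. State whether the first dose means C1D1 alone or both halves, since both halves span 49–56 h against about 24 h for one injection. Give onset and resolution times in both arms. Keep the IRR and sARR tables as arm-specific description. State in protocol Section 10.3.1 which reading of the causality sentence is meant.

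Administration times (protocol Section 6.5) and AE onset times (SAP 6.3) are already planned, so no new data are needed. A rule for missing onset times is needed, because SAP 6.3 limits its imputation to classifying events as treatment emergent.

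**(b) SAP 5.5.4.1 and 5.5.4.2.** Base the Part B between-arm worst-grade and notable-value summaries on visits scheduled in both arms. Omit C1D2 from the comparison, and keep it in the listings and the GEN3014 summary. The cost is a few readings lost from the comparison.

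**(c) SAP 5.5.3.** Replace GEN3014 dose with trial drug dose. Aligning the post-treatment SAE sentence in SAP 5.5.2.1 with protocol Section 8.4.6, which already refers to trial drug, is a wording change only.
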